3.6. Safety analysis

All subjects included in the safety analyses will be evaluated by the actual treatment arms unless otherwise specified.

3.6.1. Adverse Events

A treatment-emergent adverse event (TEAE) is defined as any untoward medical occurrence in a subject who received IMP, which occurs within the period from the S95014 Infusion (i.e. Day 3), until the withdrawal/end-of-study visit, which is at least 30 days after S95014 infusion (i.e. Day

33) and before starting the consolidation phase. TEAE will be assessed according to the National Cancer Institute (NCI) Common Terminology Criteria Adverse Events (CTCAE) v5.0. Laboratory abnormalities will be classified into Common Terminology Criteria (CTC) grade according to CTCAE v5.0 and will be reported as adverse events.

Adverse events will be summarized in hierarchical tables, presenting the number and percentage of subjects having at least one AE, and having at least one AE in each primary system organ class and for each preferred term using MedDRA coding. AEs will be sorted by descending frequency, and alphabetically where frequency is tied. Such summaries will be produced for all AEs, serious adverse events (SAEs), grades 3 or 4 AEs, AEs leading to study discontinuation, and AEs leading to dose-adjustment or interruption of any of the drugs of the treatment. All of these summaries will be by system organ class, preferred term, treatment group and, in some case, maximum grade. Most of the summaries will be produced twice, once for all events regardless of study treatment relationship, and once for events suspected to be study treatment related. All deaths will be listed, and separate summaries will be produced by treatment.

All adverse events will be listed, and any other information collected (e.g., start/end dates and duration of adverse event, severity or relatedness to study medication or backbone therapies) will be listed as appropriate.

Adverse events of special interest (AEOSI) will be summarized separately. AEOSI include:

- Grade ≥ 3 ALT/AST increase or grade ≥ 3 hyperbilirubinemia
- Grade ≥ 3 haemorrhage or grade ≥ 3 thromboembolic events
- Grade ≥ 3 pancreatitis
- Grade ≥ 3 hypersensitivity

All such events will be identified prior to database lock.

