- Screening visit (up to 14 days prior to inclusion): to obtain informed consent and check the screening/non-screening criteria.
- Screening period (Day -14 to Day -1): to check the eligibility of the patient to be included and randomized in the study within 14 days prior to the inclusion.
- **Inclusion visit (Day 0)**: to check inclusion/non-inclusion criteria and to confirm inclusion of the patient in the study
- Randomization (Day 3): the day of S95014 infusion (i.e. Day 3), included patients will be randomly assigned to one of the two treatment groups:
  - Lyophilized S95014 (arm 1)
  - Liquid S95014 (arm 2)
- **Treatment period:** treatment period will start from the day of S95014 infusion, corresponding to Day 3 of the induction phase, until the withdrawal/end-of-study visit.
- Withdrawal/End-of-study visit: at least 30 days after S95014 infusion (i.e. Day 33) and before starting the consolidation phase. During the withdrawal/end-of-study visit, patients will be proposed to participate in a roll-over study (CL2-95014-003) for the consolidation phase using lyophilized S95014 in combination with backbone regimen as per ALL-MB 2015 protocol.

The study start is defined as the date of the first visit of the first participant.

End of Trial is defined as the date of the last visit of the last participant.

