### 4.4. Discontinuation of the study or temporary halt

### 4.4.1. Premature discontinuation of the study or temporary halt

This study may be temporarily halted or prematurely discontinued at any time for any sufficient reasonable cause.

After having informed the national coordinator, the sponsor or the Independent Ethics Committee (IEC) or the Competent Authority may terminate the study before its scheduled term. Two copies of the written confirmation will be dated and signed by the national coordinator. The IEC and Competent Authority will be informed according to local regulations.

If the study is prematurely discontinued, the on-going participants should be seen as soon as possible, and the same assessments as described in section 5.8 should be performed.

Under some circumstances, the investigator may be informed of additional procedures to be followed in order to ensure that adequate consideration is given to the protection of the participant's interests.

In case of study suspension (temporary halt), the study may resume once concerns about safety, protocol compliance, data quality are addressed and satisfy the Sponsor, the Independent Ethics Committee (IEC) and Competent Authority.

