# 8.7. Definition of Events requiring an immediate notification (ERIN)

An event must be **notified immediately** (i.e. without delay and within 24 hours at the latest) to the sponsor if it is:

- a serious adverse event,
- an adverse event of special interest, (if applicable, as defined in § 8.6, otherwise delete)
- an overdose of the IMP/NIMP even if asymptomatic,
- any intake of the IMP/NIMP by a person around the participant,
- a pregnancy.

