# 8.9. Reporting procedures

#### 8.9.1. Time frame for AE reporting

Any event meeting the above mentioned definitions (see sections 8.3 to 8.7) must be reported to the sponsor on an adverse event form if it occurred:

- before the first intake of the IMP for events related to the research
- at any time after the administration of IMP, up to the participant's last study visit for all events.
- up to 30 calendar days after the IMP administration for all ERIN, regardless of the supposed role of the research,
- irrespective of the time of onset in case of serious adverse event related to the research.

Of note, events occurring between the signature of the informed consent and the first administration of the IMP for which the investigator does not consider an association with any procedure/condition required by the study protocol must be reported as medical history or as signs and symptoms related to the studied disease in the dedicated form of the CRF.

<sup>1 Instrumental Activities of Daily Living (ADL) refer to preparing meals, shopping for groceries or clothes, using the telephone, managing money, etc.

<sup>2 Self-care ADL refer to bathing, dressing and undressing, feeding self, using the toilet, taking medications, and not bedridden".

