# 8.9.2.2. Follow-up of adverse events

The investigator must ensure that follow-up of the participant is appropriate to the nature of the event, and that it continues until resolution if deemed necessary.

Any change in terms of diagnosis, intensity, seriousness, measures taken, causality or outcome regarding an adverse event already reported must be written up in a new complete evaluation of the event documented on an "Adverse event" page previously created for the event.

If the adverse event has not resolved at the participant's final visit in the study, the participant must be followed up suitably and any information on the outcome of the event will be noted on an « Adverse Event » page previously created for the event

If the follow-up of the participant is not done by the investigator him/herself (hospitalisation, followed by a specialist or the participant's general practitioner, ...), the investigator will do everything to establish/maintain contact with the person/department in charge of follow-up of the participant.

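### SAP 3.6.1 defines treatment-emergent events by occurrence after infusion only, so a reported pre-infusion AE that worsens after S95014 is not classified as a TEAE

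*SAP*

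**What the plan says.** **The definition.** SAP 3.6.1 counts as a TEAE an untoward occurrence in a dosed subject "which occurs within the period from the S95014 Infusion (i.e. Day 3), until the withdrawal/end-of-study visit". The same sentence describes that visit: "which is at least 30 days after S95014 infusion (i.e. Day" 33). It says nothing about worsening. The protocol uses the term but defines it neither among its AE definitions (8.3) nor in its AE analysis (10.2.2.1). The secondary safety objective is stated in TEAEs (Protocol 3.2, SAP 1.1.2).

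**What goes on an AE page.** Under Protocol 8.9.1, an event before the infusion is reported on the AE form only if it is related to the research; otherwise it goes to medical history or disease signs and symptoms. Protocol 8.8 counts a product other than the IMP taken under the protocol (NIMP) as a research relation, and Protocol 6.1.2 makes the backbone drugs NIMPs.

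**Changes in a reported event.** Protocol 8.9.2.2: "Any change in terms of diagnosis, intensity, seriousness, measures taken, causality or outcome regarding an adverse event already reported must be written up", as a new evaluation on the page already opened for that event. By contrast, Protocol 8.3 and 8.9.2.4 make worsening of a condition present at study entry an AE in its own right.

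**End of collection.** Protocol 8.9.1 collects AEs "at any time after the administration of IMP, up to the participant's last study visit for all events". It also collects events requiring immediate notification (ERIN), which under 8.7 include SAEs and adverse events of special interest (AEOSI), "up to 30 calendar days after the IMP administration for all ERIN, regardless of the supposed role of the research". Protocol 4.1.1 places the withdrawal/end-of-study visit "at least 30 days after S95014 infusion (i.e. Day 33) and before starting the consolidation phase". If the whole study stops early, Protocol 4.4.1 says "the on-going participants should be seen as soon as possible".

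**The concern.** S95014 is given on Day 3 of an induction that includes other cytotoxic drugs and steroids. An event attributed to one of those drugs, or to a study procedure, can be open on an AE page before the infusion and become severe after it. A treatment-emergent definition is meant to catch that rise. This one does not, because it asks only whether the event occurs from the infusion onward.

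The result then depends on the form used. The same clinical course counts if the condition was present at study entry and does not count if it was already reported as a research-related AE. This matters most for AEOSI, which are defined by reaching grade 3, so crossing that grade after dosing is the event of interest.

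The end of the window raises a smaller question. It is tied to a visit, whereas the ERIN rule is tied to 30 days after dosing, and the two agree only if the visit is held when both documents say.

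**Working it through.** **1. The plan's own figure.** Infusion on Day 3 plus 30 days gives Day 33. This reproduces the earliest withdrawal/end-of-study visit in Protocol 4.1.1 and SAP 3.6.1.

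**2. Worsening, case by case.**

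| Course | Form used before infusion | How worsening after infusion is recorded | TEAE under SAP 3.6.1? |
|---|---|---|---|
| New event after infusion | None | New AE page | Yes |
| Condition present at study entry, worsens | Medical history | As an AE (Protocol 8.3; 8.9.2.4 for chronic disease) | Yes |
| Research-related AE between consent and infusion, worsens | AE page (8.9.1) | New evaluation on the same page (8.9.2.2) | No, by onset date |
| Unrelated event between consent and infusion, worsens | Medical history, or signs and symptoms (8.9.1) | Not clear: 8.3 speaks of conditions present at entry | Unclear |

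The third row is the gap. The paper fallback in Protocol 8.9.2.5 works the same way: a worsening to serious goes on an additional-information page for the same event.

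**3. Where such an event still appears.** SAP 3.6.1 lists all AEs and describes tables for all AEs, SAEs and grade 3 or 4 AEs, with a separate AEOSI summary. None is expressly limited to TEAEs. SAP 3.6.2 plans shift tables from baseline to the worst treatment-period laboratory value by CTCAE grade. The loss is therefore the TEAE label.

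**4. Size.** Planned inclusion is 88 patients at 1:1, so 88 / 2 = 44 per arm, assuming all are dosed. One misclassified patient with no other TEAE in the same table row changes that row by 1/44 = 2.3 percentage points. The documents give no rate. For an assumed one, two or four such patients in an arm:

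- 1/44 = 2.3 points
- 2/44 = 4.5 points
- 4/44 = 9.1 points

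These counts are illustrative only.

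**5. End of window (conditional).** Let x be the days from infusion to the last visit. ERIN days collected but outside the TEAE window = max(0, 30 − x).

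| Last visit | x | Uncovered days |
|---|---|---|
| Day 33 or later | 30 or more | 0 |
| Day 24 | 21 | 9 |
| Day 17 | 14 | 16 |
| Day 10 | 7 | 23 |
| Day 3 | 0 | 30 |

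The early visit dates are assumed; the documents give neither the rate nor the timing of early withdrawal.

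**The case against.** **No event disappears.** As step 3 shows, the SAP lists every AE and does not confine its tables to TEAEs. This stands, and it limits the consequence to the TEAE count. It does not remove the fault. If the tables are meant to be TEAE tables, the events in question are left out. If they are all-AE tables, pre-infusion events that never worsened are mixed in and no table delivers the stated objective.

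**Laboratory worsening is covered.** Largely true. The shift tables capture it whichever form was used. Protocol 8.2 also makes a laboratory abnormality an AE only if it is symptomatic, clinically significant, treated, or linked to delay or discontinuation, so a bare grade 1 rise would not ordinarily have an AE page before infusion. Clinical events such as thrombosis or pancreatitis are not in the shift tables.

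**Pre-infusion onset is an inference.** Protocol 8.9.2.2 does not say which date fixes treatment-emergent status. That is fair, but the SAP offers no other rule, and onset date is the natural reading of its wording. The backbone calendar (Appendix 1) is not reproduced in the text, so exposure before Day 3 cannot be itemised.

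**The visit cannot fall inside 30 days.** As written, both documents place it at Day 33 or later, and on that reading the second gap is zero. Support for an earlier last visit is indirect: discontinuation for adverse events, consent withdrawal or physician decision (Protocol 5.8.1), discontinuation after serious hypersensitivity (8.6.4), the early-stop provision in 4.4.1, and the separate 30-day ERIN rule, which adds little unless a last visit can come sooner. That rule may simply be template text. The point therefore stays conditional.

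**Safety is secondary and descriptive.** True. The primary PK conclusion is untouched.

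**Conclusion.** The definition is incomplete and should be corrected. A research-related AE reported before the infusion that increases in grade afterwards is not classified as treatment-emergent, while worsening of a condition present at entry is. The effect is on the TEAE count behind the secondary safety objective: about 2.3 percentage points per misclassified patient in an arm of 44, in a group that is probably small and whose rate is unknown. This assumes that TEAE status is derived from the onset date on the AE page and that all 88 patients are dosed.

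The end-of-window gap is secondary. It is zero for any visit on or after Day 33 and appears only if a last visit is held sooner.

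Three stronger readings are tempting:

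- *The SAP discards these events.* It does not: they remain in the listing and, as written, in the all-AE and AEOSI tables.
- *The TEAE window is generally shorter than the ERIN window.* Both documents put the visit at least 30 days after infusion.
- *The comparison of arms is biased.* The rule is the same in both arms, and the pre-infusion event arises before either formulation is given. A true difference in worsening could be partly missed, but nothing in the documents points to one.

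**What to change.** In SAP 3.6.1, define a TEAE as *an AE that starts, or worsens in CTCAE grade compared with its last grade before the infusion, between the start of the S95014 infusion and the later of the withdrawal/end-of-study visit and 30 days after the infusion*. Derive the grade change from the successive evaluations kept under Protocol 8.9.2.2. The 30-day term also closes the window for a patient with no final visit, for whom the present wording gives no end date.

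For each AE, SAE and AEOSI table, state whether it uses TEAEs or all AEs, so that at least one set clearly answers the TEAE objective. Say also how an unrelated event that arose between consent and infusion, and was entered as medical history or signs and symptoms, is handled if it worsens.

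The cost is SAP wording and programming. The data for the new definition are already collected, and no visit, sample or clinical rule changes. TEAE counts may rise slightly. The change should be made before database lock.

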3.6.2. Other Safety Evaluations

Descriptive statistics of laboratory parameters and continuous variables of vital signs will be calculated by treatment group for each time point. Shift tables for qualitative urinalysis results at each time point after the start of administration will be created. Height, weight, body surface area (BSA) and body mass index (BMI) will be summarized over visit by treatment group.

Shift tables will be provided for laboratory parameters to compare a subject's baseline laboratory evaluation relative to the worst value during the treatment period using Common Terminology Criteria for Adverse Events (CTCAE) v5.0 grades. In addition, the normal laboratory ranges will be used to evaluate whether a particular laboratory test value was normal, low, or high for each visit value relative to whether or not the baseline value was normal, low, or high. Subjects with abnormal laboratory values will be listed and values outside the normal ranges will be flagged.

3.7. Analysis of Plasma Asparaginase Activity

Observed individual Plasma Asparaginase Activity (PAA) level 7 days (Day 10), 14 days (Day 17), 18 days (Day 21) and 25 days (Day 28) after administration of either liquid or lyophilized S95014 will be tabulated by treatment group together with descriptive statistics (Arithmetic mean, SD, geometric mean, geometric CV, median, min, max).

The number and proportion of subjects achieving a PAA of ≥ 0.1 U/mL after the administration of either liquid or lyophilized S95014 among subjects with evaluable Day 10, Day 17, Day 21 and Day 28 PAA data will be summarized by treatment group along with a 2-sided 95% Clopper-Pearson confidence interval (CI).

3.8. Immunogenicity Analysis

The immunogenicity analysis will be performed on the Immunogenicity Analysis Set (IAS). The assessment of anti-drug antibodies includes binding and neutralizing antibodies to S95014 and binding anti-PEG antibodies.

The number and proportion of subjects in the immunogenicity analysis set having anti S95014 \pm anti-PEG antibodies at pre-dose, and 14 and 25 days (i.e. Day 17 and Day 28) after the administration of either liquid or lyophilized S95014 during the induction phase will be summarized by treatment group.

Results will be reported as follows:

- Pre-existing anti-S95014 or anti-PEG antibodies: number and proportion of samples confirmed positive at baseline.
- Seroconversion upon treatment: number and proportion of samples converted from negative at baseline to positive at Day 17 and Day 28. If a confirmed positive sample at baseline has titer increase at Day 17 or Day 28 by at least 4-fold (boosted ADA responses) then it will be included within the seroconverters. If a patient was negative at baseline, and ended up with a positive titer of "2" for example, post-treatment, this case was considered as a seroconversion despite the fact that the titer was not a 4 fold rise.

On a case-by-case approach, the impact of positive anti S95014 and anti-PEG antibodies will be investigated:

- On the pharmacokinetics through the temporal association of antibodies with the loss of asparaginase activity (neutralizing antibodies)
- On the safety through the temporal relationship with treatment-emergent hypersensitivity and anaphylactic reactions.

A patient with missing baseline will be considered as negative baseline to be conservative.

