## 10.2.5. Immunogenicity Analysis

The assessment of anti-drug antibodies includes binding and neutralizing antibodies to S95014 and binding anti-PEG antibodies.

The number and proportion of patients having anti S95014  $\pm$  anti-PEG antibodies 14 and 25 days (i.e. Day 17 and Day 28) after the administration of either liquid or lyophilized S95014 during the induction phase will be summarized by treatment group.

Results will be reported as follows:

- Pre-existing anti-S95014 or anti-PEG antibodies: number and proportion of samples confirmed positive at baseline.
- Seroconversion upon treatment: number and proportion of samples converted from negative at baseline to positive at Day 17 and Day 28. If a confirmed positive sample at baseline has titer increase at Day 17 or Day 28 by more than 4-fold then it will be included within the seroconverters.

On a case-by-case approach, the impact of positive anti S95014 and anti-PEG antibodies will be investigated:

- On the pharmacokinetics through the temporal association of antibodies with the loss of asparaginase activity (neutralizing antibodies)
- On the safety through the temporal relationship with treatment-emergent hypersensitivity and anaphylactic reactions.

A patient starting with pre-existing antibodies (positive baseline) will not be considered for positive post-baseline anti-drug antibodies. A patient with missing baseline will be considered as negative baseline to be conservative.

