5. APPENDICES**6. CHANGES FROM THE PLANNED STATISTICAL ANALYSIS**

Not applicable.

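### Protocol 10.2.5 and SAP 3.8 set different rules for who counts as a seroconverter, and neither defines an any-time, patient-level treatment-emergent antibody rate

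*SAP*

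**What the plan says.** **Unit.** Both documents use the same words. SAP 3.8 reports seroconversion as the "number and proportion of samples converted from negative at baseline to positive at Day 17 and Day 28", and Protocol 10.2.5 has the same wording. Neither gives a denominator or says whether the proportion is per visit or across visits.

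**Boost rule for baseline-positive patients.** Protocol 10.2.5 counts such a sample if it has a "titer increase at Day 17 or Day 28 by more than 4-fold then it will be included within the seroconverters". SAP 3.8 counts it if the titre rises "by at least 4-fold (boosted ADA responses) then it will be included within the seroconverters".

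**Baseline-positive patients generally.** Protocol 10.2.5 ends with: "A patient starting with pre-existing antibodies (positive baseline) will not be considered for positive post-baseline anti-drug antibodies". SAP 3.8 has no such sentence.

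**Patient-level summary.** Both documents also plan the number and proportion of patients with antibodies at each visit, by treatment group. The SAP does this in the Immunogenicity Analysis Set (IAS) and adds the pre-dose visit.

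**Record of changes.** Protocol 10.5 sends changes in the planned analysis to SAP amendments. SAP section 6, on changes from the planned analysis, reads "Not applicable". SAP section 1 says the plan follows protocol v2.0 and a non-substantial amendment of 7 April 2021, which is not among the documents.

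**The concern.** Assessing the immunogenicity of both formulations is a secondary objective. The figure a reader will want is the share of patients in each arm who develop antibodies after dosing or whose existing antibodies are boosted. The plan has three rules that bear on this figure (unit, fold cut-off, handling of baseline-positive patients). Two of them differ between the documents and the third is incompletely specified.

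The SAP's only explicitly patient-level count is positivity by visit. Without the protocol's sentence, that count puts patients who were already positive before dosing together with those who became positive after it. The trial is open-label, so the choice among responder rules should be settled in writing before the data are seen by arm.

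**Working it through.** No antibody rate, baseline prevalence or immunogenicity sample size is stated, so there is no plan figure to reproduce for this endpoint. The arm size of 39 below is the evaluable number per arm in SAP 1.3. That number itself checks: two one-sided tests with CoV 0.30, GMR 1 and 39 per arm give 90.7% power against the stated approximate 90%. It does not bear on the antibody result. The IAS could be larger than 39 per arm, up to about 44 if all 88 are treated and sampled.

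**1. Effect of the unit.** Each patient gives two post-dose antibody samples (Day 17 and Day 28). Let k of n patients convert.

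- Patient rate: k/n.
- Pooled samples, every converter positive at one visit only: k/(2n).
- Pooled samples, every converter positive at both visits: 2k/(2n) = k/n.

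With n = 39 and k = 4 (assumed), the patient rate is 4/39 = 10.3%, and the pooled sample rate lies between 4/78 = 5.1% and 8/78 = 10.3%. At a single visit there is one sample per patient, so the two units agree.

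**2. Effect of the cut-off.** Protocol 9.3 defines the titre as the highest dilution that still tests positive, so it is discrete and an exact four-fold rise is possible. The dilution step is not stated. If it is two-fold (an assumption), a rise strictly above four-fold means at least eight-fold. Each patient reclassified moves the arm by 1/39 = 2.6 points (1/44 = 2.3 points with 44 patients). With no baseline-positive patients the two cut-offs give the same answer.

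**3. Both together, on assumed counts.** Take one arm of 39:

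- 33 baseline-negative, of whom 4 convert: 2 at both visits, 1 on Day 17 only, 1 on Day 28 only. That is 2×2 + 1 + 1 = 6 positive samples.
- 6 baseline-positive, of whom 2 rise exactly four-fold and 1 rises eight-fold, all on Day 28 only.

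| Rule for baseline-positive patients | Patients, any time (95% Clopper-Pearson) | Day 17 | Day 28 | Samples, pooled |
|---|---|---|---|---|
| Not counted | 4/39 = 10.3% (2.9 to 24.2) | 3/39 = 7.7% | 3/39 = 7.7% | 6/78 = 7.7% |
| Rise above four-fold (protocol) | 5/39 = 12.8% (4.3 to 27.4) | 3/39 = 7.7% | 4/39 = 10.3% | 7/78 = 9.0% |
| Rise of four-fold or more (SAP) | 7/39 = 17.9% (7.5 to 33.5) | 3/39 = 7.7% | 6/39 = 15.4% | 9/78 = 11.5% |

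One dataset gives 7.7% to 17.9%, depending on unit and rule. The by-visit columns do not recover the any-time column, because the overlap between visits is not reported.

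**4. The SAP's by-visit patient count.** In the same arm, if all 6 baseline-positive patients are still positive on Day 28 (a further assumption), the SAP count for that visit is 3 + 6 = 9 of 39 = 23.1%, of whom 3 are newly positive. The SAP's added pre-dose count shows how many were positive beforehand, but not which of the Day 28 positives they are.

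**The case against.** The strongest reply is that one sample is taken per patient per visit and the neighbouring sentence in SAP 3.8 summarises subjects by visit, so samples may be loose wording for patients at each visit. The same paragraph goes on to speak of seroconverters and of a patient who was negative at baseline. The table shells are in a separate document that may settle this. This stands. A reader might infer that the plan double-counts patients, or that it understates the antibody rate. The documents do not support that, because no passage says Day 17 and Day 28 are pooled. What remains is that the text permits pooling and that, on the by-visit reading, no any-time patient rate is defined.

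Three other stronger readings also go too far:

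- *That the protocol flatly contradicts itself.* Its sentence on baseline-positive patients can be read as governing only the count of post-baseline positivity, leaving the boost rule to govern seroconversion. On that reading the protocol's patient count is of new antibodies only, and the mixing of old and new is confined to the SAP. The sentence still needs clarifying, because its scope is not stated.
- *That SAP section 6 is wrong.* The amendment of 7 April 2021 might have changed Protocol 10.2.5. That cannot be checked here.
- *That a planned comparison between arms is compromised.* The objective is to assess immunogenicity, and no antibody test or margin is planned.

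It is also fair that the cut-off touches few patients. It matters only for an exact four-fold rise from a positive baseline, in newly diagnosed patients among whom baseline positivity may be uncommon.

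**Conclusion.** The point holds as a conflict and a gap in the definition of a descriptive secondary result. The two documents give different boost cut-offs, the SAP omits a protocol rule on baseline-positive patients without recording it (unless the unseen amendment does), and the unit and denominator of the seroconversion proportion are not settled. As written, neither document yields the share of patients with treatment-emergent antibodies at any time.

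Its size depends on data not yet known. Pooling visits could reduce the figure to as little as half the patient rate. Each baseline-positive patient classed differently moves a 39-patient arm by 2.6 points. In the assumed example, going from not counting baseline-positive patients to the SAP cut-off moves the patient rate by 3/39 = 7.7 points, which is smaller than the sampling uncertainty in an arm of this size. The primary PK comparison and the sample size are untouched. It is worth correcting because the correction is nearly free and because any later choice among the rules would be made with open-label data in hand.

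**What to change.** In SAP 3.8, report per arm, with IAS patients as the stated denominator, both by visit and at any time:

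- treatment-induced: baseline negative, positive at Day 17 and/or Day 28;
- treatment-boosted: baseline positive, with a titre rise meeting one stated fold cut-off;
- the total of the two.

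Keep the existing by-visit positivity counts as supportive. Use the same cut-off in both documents, with its inclusive or exclusive form spelled out. Reconcile the protocol sentence on baseline-positive patients with the boost rule, stating which count it governs. Record the departure from protocol v2.0 in SAP section 6, unless the 7 April 2021 amendment already covers it, in which case cite it there.

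Cost: a few lines of wording and one table. No new samples, visits or assays are needed.
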